11.3. Appendix 3: Assessment Windows

11.3.1. Definitions of Assessment Windows for Efficacy Analyses

Analysis Set / Domain	Parameter (if applicable)	Target Number of Days from Day 1 in each TC	Analysis Window		Analysis Timepoint
			Beginning Timepoint	Ending Timepoint	
e.g. "Safety", "Efficacy" or list specific domains if required	e.g. "All" or list specific parameters (i.e. tests) if required	The target or most desired relative day or relative time value for a given visit. e.g. "Day 7"	e.g. "Day 1"	e.g. "Day 10"	e.g. VISIT 1
Efficacy		Study Baseline		Day 1 [1]	Study Baseline
Efficacy		Day 15	Day 2	Day 22	TC1 Week 2
Efficacy		Day 43	Day 23	Day 64	TC1 Week 6
Efficacy		Day 85	Day 65	Day106	TC1 Week 12
Efficacy		Day 127	Day 107	Day 148	TC1 Week 18
Efficacy		Day 169	Day149	Day190	TC1 Week 24
Efficacy		Day 211	Day191	Day 232	TC1 Week 30
Efficacy		Day 253	Day 233	Day 274	TC1 Week 36
Efficacy		Day 295	Day 275	Day 316	TC1 Week 42
Efficacy		Day 337	Day 317	Day 358	TC1 Week 48
Efficacy		Day 1	Latest pre-dose assessment before 2 nd treatment [2]		TC2 Week 0
Efficacy		Day 15	Day 2	Day 22	TC2 Week 2
Efficacy		Day 43	Day 23	Day 64	TC2 Week 6
Efficacy		Day 85	Day 65	Day106	TC2 Week 12
Efficacy		Day 127	Day 107	Day 148	TC2 Week 18
Efficacy		Day 169	Day149	Day190	TC2 Week 24
Efficacy		Day 211	Day191	Day 232	TC2 Week 30
Efficacy		Day 253	Day 233	Day 274	TC2 Week 36
Efficacy		Day 1	Latest pre-dose assessment before 3 rd treatment [2]		TC3 Week 0
Efficacy		Day 15	Day 2	Day 22	TC3 Week 2
Efficacy		Day 43	Day 23	Day 64	TC3 Week 6
Efficacy		Day 85	Day 65	Day106	TC3 Week 12
Efficacy		Day 127	Day 107	Day 148	TC3 Week 18
Efficacy		Day 169	Day149	Day190	TC3 Week 24

NOTES :

- [1] prior to treatment. If the date of assessment of efficacy endpoint is the same as the date of treatment, this can be regarded as prior to treatment according to study protocol.
- [2] typically to use data of qualification for re-treatment

CONFIDENTIAL

204947

Analysis Set / Domain	Parameter (if applicable)	Target Number of Days from Day 1 in each TC	Analysis Window		Analysis Timepoint
			Beginning Timepoint	Ending Timepoint	

- Day 1 is the treatment date in each TC

11.3.2. Definitions of Assessment Windows for Safety Analyses (only Week 48 visit and Withdraw visit)

Table below shows the assessment window which applied to safety data at week 48 visit and withdrawal visit. Safety data at week 48 visit or withdrawal visit will be used as data of the visit within an assessment window, only if safety data for the planned scheduled visit is missing.

This assessment window will not be applied to any safety data at other visits. This means safety data except for week 48 visit and withdrawal visit will be only used as visit collected in eCRF.

Note that as described in section 8, safety data at last visit (typically, this is week 48 visit or withdrawal visit) will be also treated as study exit.

Rationale: For example, if a given subject receive 2nd treatment at week 36 after 1st treatment and complete study (i.e., complete week 48 visit), data for week 48 visit will be entered in “Week 48” page in eCRF, not in “Week 12 from 2nd treatment” page. In this case, data for week 12 from 2nd treatment seems to be missing in eCRF, but this is not true. This is the case for other situations. In order to summarize safety data at week 48 visit or withdrawal visit appropriately in a given TC or GTCs, this assessment window is needed.

Analysis Set / Domain	Parameter (if applicable)	Target Number of Days from Day 1 in each TC/GTC	Analysis Window		Analysis Timepoint in appropriate study phase (TC1 or GTCs)
			Beginning Timepoint	Ending Timepoint	
e.g. “Safety”, “Efficacy” or list specific domains if required	e.g. “All” or list specific parameters (i.e. tests) if required	The target or most desired relative day or relative time value for a given visit. e.g. “Day 7”	e.g. “Day 1”	e.g. “Day 10”	e.g. VISIT 1
Safety		Day 15	Day 12	Day 18	Week 2
Safety		Day 43	Day 36	Day 50	Week 6
Safety		Day 85	Day 78	Day 92	Week 12
Safety		Day 127	Day 120	Day 134	Week 18
Safety		Day 169	Day 162	Day 176	Week 24
Safety		Day 211	Day 204	Day 218	Week 30

CONFIDENTIAL

204947

Analysis Set / Domain	Parameter (if applicable)	Target Number of Days from Day 1 in each TC/GTC	Analysis Window		Analysis Timepoint in appropriate study phase (TC1 or GTCs)
			Beginning Timepoint	Ending Timepoint	
Safety		Day 253	Day 246	Day 260	Week 36
Safety		Day 295	Day 288	Day 302	Week 42
Safety		Day 337	Day 330	Day 343	Week 48

NOTES :

- Day 1 is the treatment date in each TC/GTC

11.4. Appendix 4: Study Phases and Treatment Emergent Adverse Events

11.4.1. Study Phases

Assessments and events will be classified according to time of occurrence relative to the start date of the study treatment and/or study withdraw date. In both efficacy and safety data, TC1 is double blind phase and the period after receiving 2nd treatment is open label phase as study design.

11.4.1.1. Study Phases for Efficacy Data

Treatment State	Definition
Pre-Treatment	Date \leq 1st treatment Date
Treatment Cycle 1 (TC1)	1st treatment Date $<$ Date (if the subject completes / withdraws without 2nd treatment) \leq Study Exit/Withdraw Date or (if the subject take 2nd treatment) \leq 2nd treatment Date
Treatment Cycle 2 (TC2)	2nd treatment Date $<$ Date (if the subject completes / withdraws without 3rd treatment) \leq Study Exit/Withdraw Date or (if the subject take 3rd treatment) \leq 3rd treatment Date
Treatment Cycle 3 (TC3)	3rd treatment Date $<$ Date \leq Study Exit/Withdraw Date

NOTES:

- If the date of assessment of efficacy endpoint is the same as the date of 1st treatment, this can be regarded as prior to treatment according to study protocol.

11.4.1.2. Study Phases for AE Data and Safety Date except for AE

Treatment State	Definition
Pre-Treatment	AE Start Date $<$ 1st treatment Date
On-Treatment	If AE onset date is on or after treatment start date & on or before treatment stop date. 1st treatment Date \leq AE Start Date \leq Study Treatment Stop Date
Onset Time Since 1st Dose (Days)	If 1st treatment Date $>$ AE Onset Date = AE Onset Date - 1st treatment Date If 1st treatment Date \leq AE Onset Date = AE Onset Date - 1st treatment Date +1 Missing otherwise.
Duration (Days)	AE Resolution Date - AE Onset Date + 1
Treatment Cycle 1 (TC1) \leq 84 days from 1st treatment	1st treatment Date \leq AE Start Date \leq 1st treatment Date +83
Treatment Cycle 1 (TC1)	1st treatment Date \leq AE Start Date (if the subject completes / withdraws without 2nd treatment) \leq Study Exit/Withdraw Date

CONFIDENTIAL

204947

Treatment State	Definition
	or (if the subject take 2nd treatment) < 2nd treatment Date
GSK1358820 Treatment Cycle 1 (GTC1)	For subjects who received GSK1358820 as 1st treatment: 1st treatment Date ≤ AE Start Date (if the subject completes / withdraws without 2nd treatment) ≤ Study Exit/Withdraw Date or (if the subject take 2nd treatment) < 2nd treatment Date For subjects who received placebo as 1st treatment: 2nd treatment Date /Time ≤ AE Start Date / Time (if the subject completes / withdraws without 3rd treatment) ≤ Study Exit/Withdraw Date or (if the subject take 3rd treatment) < 3rd treatment Date
GSK1358820 Treatment Cycle 2 (GTC2)	For subjects who received GSK1358820 as 1st treatment: 2nd treatment Date /Time ≤ AE Start Date / Time (if the subject completes / withdraws without 3rd treatment) ≤ Study Exit/Withdraw Date or (if the subject take 3rd treatment) < 3rd treatment Date For subjects who received placebo as 1st treatment: 3rd treatment Date / Time ≤ AE Start Date / Time ≤ Study Exit/Withdraw Date
GSK1358820 Treatment Cycle 3 (GTC3)	For subjects who received GSK1358820 as 1st treatment: 3rd treatment Date / Time ≤ AE Start Date / Time ≤ Study Exit/Withdraw Date For subjects who received placebo as 1st treatment: Not applicable because 3 rd treatment of GSK1358820 is not allowed for subjects who received placebo as 1st treatment
Overall	For subjects who received GSK1358820 as 1st treatment 1st treatment Date ≤ AE Start Date ≤ Study Exit/Withdraw Date For subjects who received placebo as 1st treatment 2nd treatment Date ≤ AE Start Date ≤ Study Exit/Withdraw Date

NOTES:

- If the study withdraw date is missing then the AE will be considered to be On-Treatment.
- AE start time needs to be considered if AE start date is equal to the re-treatment date
- As for safety date except for AE (i.e., laboratory data etc.), "AE Start Date" will be replaced with the date of measurement, unless otherwise specified.

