8.1. Adverse Events Analyses

Adverse events analyses including the analysis of adverse events (AEs), Serious (SAEs) and other significant AEs will be based on GSK Core Data Standards. The details of the planned displays are provided in [Appendix 10: List of Data Displays](#).

All AEs will be classified using the standard GSK Medical Dictionary for Regulatory Activities (MedDRA) dictionary, and grouped by SOC and PT, unless otherwise stated. The investigator will evaluate all AEs with respect to seriousness, severity, and causality.

AEs analyses will be by treatment group (and total for GTC1, GTC2, GTC3 and Overall) and study phases (i.e., TC1, TC1 <= 84 days, GTC1, GTC2, GTC3 and Overall, see section [11.4](#)). Note that Overall includes all AEs after GSK1358820 treatment.

The number and percentage of subjects experiencing an AE and the total number of AEs (the number of subjects with any AEs) will be summarized for each of the following AE categories by treatment group (and total for GTC1, GTC2, GTC3 and Overall):

- All AEs (by SOC and PT; by SOC and PT and maximum severity)
- Common AEs (by PT)
- Serious AEs (by SOC and PT)

CONFIDENTIAL

204947

- Treatment related AEs (by SOC and PT; by SOC and PT and maximum severity)
- Study drug related AEs (by SOC and PT; by SOC and PT and maximum severity)
- Injection related AEs (by SOC and PT; by SOC and PT and maximum severity)
- Fatal serious AEs (by SOC and PT)
- AEs resulting in withdrawal from study (by SOC and PT)
- Serious treatment related AEs (by PT, for PLS)
- Non-serious treatment related AEs (by PT, for PLS)

The tabular summary for each category of AE listed above will include the number of subjects who reported at least one event, and percentage of subjects who reported at least one AE (incidence) by treatment group (and total for GTC1, GTC2, GTC3 and Overall) for each SOC (where applicable), each PT, and overall. By default, adverse events will be sorted by MedDRA SOCs, in descending order from the SOC with the highest total incidence (i.e., summed across all treatment groups) for any adverse event within the class, to the SOC with the lowest total incidence. If the total incidence for any two or more adverse events is equal, the events will be presented in alphabetical order. Only SOCs with observed AE PTs will be presented. Repeat sort order for MedDRA PTs within each SOC.

Common AEs will be defined as $\geq 5\%$ in overall frequency.

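### Re-treatment-day AEs: the cycle bounds do not meet, so an AE starting before the injection falls in no cycle or in the previous one, and an AE with no start time has no rule

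*SAP*

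**What the plan says.** All references are to the amended SAP unless stated. Section 11.4.1.2 defines the phases used for AE tables.

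- **End of the earlier cycle.** TC1, and GTC1 for subjects who received active drug first, end at "or (if the subject take 2nd treatment) < 2nd treatment Date". The next cycle ends in the same way: "or (if the subject take 3rd treatment) < 3rd treatment Date". Both bounds are strict and use the date only.
- **Start of the next cycle.** GTC1 for placebo-first subjects and GTC2 for active-first subjects start at "2nd treatment Date /Time ≤ AE Start Date / Time". The cycle after the third treatment is "3rd treatment Date / Time ≤ AE Start Date / Time ≤ Study Exit/Withdraw Date". These lower bounds use date and time.
- **First treatment.** The lower bound is the treatment date, inclusive, with no time.
- **Overall, placebo-first.** "2nd treatment Date ≤ AE Start Date ≤ Study Exit/Withdraw Date", by date only. Section 8.1 describes the same period as "Note that Overall includes all AEs after GSK1358820 treatment".
- **Note under the table.** "AE start time needs to be considered if AE start date is equal to the re-treatment date".

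Two other sections meet the same boundary. Section 11.6.2 ends TC1 follow-up on the day before the second treatment. Section 8.5.2 gives the re-treatment day to the next cycle when catheterization runs across a re-treatment.

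**The concern.** A set of phase definitions should place each AE in exactly one cycle. Here the end of one cycle and the start of the next use different clocks, which leaves part of the re-treatment day uncovered.

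An AE in that part of the day is plausible. Protocol 6.1.2.2 allows urethral anaesthesia, sedation and a bladder instillation that stays in place for at least 15 minutes. Under 6.1.2.3 a cystoscope is then passed before the needle is used. By re-treatment, AE collection has been running since the first treatment, so such an event will be recorded and will need a cycle.

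Safety of repeated dosing is a stated objective, and injection-procedure-related AEs are tabulated by cycle (Tables 3.18, 3.28, 3.38 and 3.48). Two programmers working from this text could produce different per-cycle tables. One of those versions would charge an event from an open-label procedure to double-blind placebo.

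**Working it through.** No power or sample-size figure is involved. The check applies the written bounds to test cases.

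**Inputs.** First treatment is Day 1. At least 84 days must elapse before re-treatment (protocol 5.3), so the earliest second treatment is Day 1 + 84 = Day 85. Take the second treatment on Day 85 and the third on Day 169 (85 + 84), each at 10:00. The clock times are illustrative.

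**Literal bounds, placebo-first subject, AE on Day 85 at 08:00.**
- TC1: is 85 < 85? No.
- GTC1: is Day 85 10:00 ≤ Day 85 08:00? No.
- Overall: is 85 ≤ 85? Yes.

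The AE is in Overall and in no cycle.

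**Both readings, both arms.** By time means that the upper bounds are also taken as date and time, as the note suggests.

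| Subject | AE onset | Literal bounds | By time |
|---|---|---|---|
| Placebo-first | Day 85, 08:00 | no cycle | TC1 |
| Placebo-first | Day 85, 11:00 | GTC1 | GTC1 |
| Placebo-first | Day 85, no time | not TC1; GTC1 undefined | TC1 and GTC1 undefined |
| Placebo-first | Day 169, 08:00 | no cycle | GTC1 |
| Active-first | Day 85, 08:00 | no cycle | TC1 and GTC1 |
| Active-first | Day 85, 11:00 | GTC2 | GTC2 |
| Active-first | Day 85, no time | not TC1 or GTC1; GTC2 undefined | TC1, GTC1 and GTC2 undefined |
| Active-first | Day 169, 08:00 | no cycle | GTC2 |

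Every row is in Overall. For active-first subjects TC1 and GTC1 are the same period, so appearing in both is not double counting.

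**What the note settles.** It says that time matters on this date. It does not alter the strict date bound, name a cycle for the earlier AE, or deal with a missing time. Section 11.7.2.1 covers missing AE dates but not missing times.

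**Conflict with follow-up.** On the by-time reading, the Day 85 08:00 AE of the placebo-first subject is a TC1 event. Section 11.6.2 ends that subject's TC1 follow-up on Day 84.

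**What is not affected.** The 84-day window runs to the first treatment date + 83, which is Day 84. The earliest re-treatment is Day 85, so no re-treatment-day AE can enter Tables 3.1 to 3.9.

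**Scale.** The documents give no count of re-treatments, re-treatment-day AEs or missing times. The ceiling on re-treatment days is 240 subjects × 2 = 480. As assumptions only, 100 re-treatments with 1% affected gives 1 AE, and 250 with 3% gives 7.5.

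**The case against.** The best defence is that the note already resolves the matter. Its natural reading is a split by time, and on that reading no timed AE is lost. Section 11.4.1 points the same way, because it starts the open-label phase after the second treatment is received. This stands as far as intent goes, and it means that falling in no cycle is certain only on the literal bounds. It does not repair the written bound, supply a rule for a missing time, or remove the conflict with follow-up time.

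It can also be said that nothing shows an AE time may be blank. The eCRF is not in the documents, so this cannot be settled either way, and a default costs nothing.

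A reader might infer that procedure-related AEs of repeat doses are systematically undercounted, so that re-treatment looks better tolerated than first treatment. The documents do not support that:

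- AEs at or after the injection time enter the new cycle. Only those starting earlier that day, or with no time, are exposed.
- The documents do not say whether the recorded treatment time is the first needle entry or the start of the procedure. If it is the latter, anaesthetic and cystoscope events already fall in the new cycle.
- The contrast with Day 1 is weak. The first-treatment bound would accept a pre-injection AE, but protocol 7.4.1.1 collects AEs only from the start of study treatment, and earlier occurrences may go to medical history.

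Nor is it an error in itself that cycle tables fail to sum to Overall. They count subjects with at least one event, in populations with different denominators.

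**Conclusion.** The inconsistency is real and lies in a stated rule. On a re-treatment date, an AE before the injection is either unassigned (literal bounds) or placed in the earlier cycle (note read as a split by time). An untimed AE is undetermined on both readings. For placebo-first subjects, Overall also admits AEs that precede their first active injection, contrary to its description in 8.1.

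The consequences are confined to the per-cycle safety tables. Overall (including Table 3.58 for procedure-related AEs), the all-AE listing (Listing 15), the tables for the first 84 days and all efficacy analyses are unaffected. The number of AEs involved cannot be derived from the documents. It is probably small, and the 1 to 7.5 shown above rests wholly on assumed inputs. The point is worth correcting because the rule is ambiguous and cheap to fix, and not because a bias in repeat-dose tolerability has been shown.

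**What to change.** Use one boundary on both sides, by date:

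- New cycle: re-treatment date ≤ AE start date.
- Earlier cycle: AE start date < re-treatment date.
- An AE on the re-treatment date belongs to the new cycle whether or not it has a time.
- Delete the note on start time, or reword it to match.
- In 8.1, describe Overall as including AEs from the date of the first GSK1358820 treatment.

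Each AE then falls in exactly one cycle, the GTC cycles together make up Overall in both arms, and the rule agrees with 8.5.2 and 11.6.2. Section 11.4.1.2 carries the AE bounds over to other safety data by measurement date, so confirm that pre-dose measurements on the re-treatment day land where intended.

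The cost is a SAP wording change and one edit to the phase derivation. The downside is that a few AEs from earlier on the re-treatment day, before the injection, count in the new cycle. For placebo-first subjects at the second treatment, they enter GTC1 and stay in Overall although they precede the first active injection. A boundary at the start of anaesthesia or cystoscopy would be finer, but the documents do not show that this time is collected.

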ECG	X e			X	X	X	X	X	X	X e	X d	X	X	X	X	X
Clinical laboratory (hematology and blood chemistry)	X				X				X	X			X		X	X
Urinalysis (dipstick)	X	X d	X	X	X	X	X	X	X	X	X d	X	X	X	X	X
Urinalysis (clinical laboratory) / Urine culture / sensitivity f	X	X d	X	X	X	X	X	X	X	X	X d	X	X	X	X	X
PVR	X		X	X	X	X	X	X	X	X		X	X	X	X	X
Ultrasound (kidney/bladder)	X	X e		X	X	X	X	X	X	X e		X	X	X	X	X
Pregnancy test (Only females of reproductive potential) g	X	X d	X	X	X	X	X	X	X	X	X d	X	X	X	X	X

	Treatment phase 1	Treatment phase 2														
		Re-treatment (1st)							Study exit (48 weeks after 1st treatment)	If qualification for re-treatment criteria was met (Within 21days prior to re-treatment)	Re-treatment (2nd)					With drawal
Week	If qualification for re-treatment criteria was met (Within 21days prior to re-treatment)	1st re-treatment	2	6	12	18 a	24 a	30 a			2nd re-treatment	2	6	12 a	18 a	
		Window	0	± 3 d	± 7 d	± 7 d	± 7 d	± 7 d			0	± 3 d	± 7 d	± 7 d	± 7 d	With drawal
Investigational product																
Treatment of antibiotic h		X									X					
Confirmation of day of re-treatment criteria i		X									X					
Treatment of investigational product		X j									X j					
Confirmation of qualification for re-treatment criteria i,k			X	X	X	X	X	X		X	X	X	X	X	X	
Concomitant meds / therapies	X	X	X	X	X	X	X	X	X	X	X	X	X	X	X	X

d = day (s)

- (a) Visit should not have occurred later than 48 weeks after 1st treatment. At 48 weeks after 1st treatment, study exit will be conducted.
- (b) Bladder diary must have been completed for any 3 consecutive days in the week prior to the visit. The volume voided is recorded by subjects for one 24-hour period during the 3 day diary collection period.
- (c) Measured only body weight
- (d) Performed prior to treatment
- (e) These examination can be completed at the Qualification for re-treatment visit or at any time prior to re-treatment
- (f) Urine culture and sensitivity is performed by the central laboratory when urinalysis (dipstick) results were suggestive of a urinary tract infection
- (g) If the result of urine pregnancy is suspicious, investigator (or sub-investigator) is able to conduct serum pregnancy test by central laboratory.

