8.3. Clinical Laboratory Analyses

Laboratory evaluations including the analyses of Chemistry laboratory tests, Hematology laboratory tests, Urinalysis, and liver function tests will be based on GSK Core Data Standards. The details of the planned displays are in [Appendix 10: List of Data Displays](#).

Clinical laboratory analyses will be by treatment group (and total for GTC1, GTC2 and GTC3) and study phases (i.e., TC1, GTC1, GTC2 and GTC3, see section [11.4](#). Note that TC1 <= 84 days and Overall will not be included for these analyses).

Raw value and change from baseline for laboratory data will be summarized by treatment group (and total for GTC1, GTC2 and GTC3) for each visit.

Shifts from baseline relative to the normal range will be also summarized by treatment group (and total for GTC1, GTC2 and GTC3) for each visit.

Worst case urinalysis results relative to baseline for protein (category: NEG, TRA, 1+, 2+, 3+, 4+) and occult blood (category: NEG, TRA, 1+, 2+, 3+) urinalysis only will be summarized by treatment group (and total for GTC1, GTC2 and GTC3) for each study phases (TC1 and GTC1, GTC2 and GTC3). The categories for worst case are: No Change/Decreased, Any Increase, Increase to TRA, Increase to 1+, Increase to 2+, Increase to 3+, Increase to 4+. The categorization is determined by comparing the baseline category to the worst case post-baseline category. The determination of the worst case post-baseline takes into account both planned and unscheduled assessments. The percentages are based on the number of subjects in the treatment group with data for the test post-baseline. Subjects with missing baseline value are to be assumed to have normal/within range baseline value.

For Chemistry and Hematology data, the scatter plots between baseline and Week12/Withdrawal will be prepared by treatment group for TC1.

In order to provide detailed information regarding liver monitoring/stopping events which are classified as adverse events in case that these events occurred, following summary and listings (IDSL number to use) will be provided.

- Summary of Hepatobiliary Laboratory Abnormalities(LIVER10)
- Listing of Medical Conditions for Subjects with Liver Stopping Events (MH2)
- Listing of Substance Use for Subjects with Liver Stopping Events (SU2)

CONFIDENTIAL

204947

- Listing of Liver Monitoring/Stopping Event Reporting(LIVER5)
- Listing of Liver Stopping Event Information for RUCAM Score(LIVER6)
- Listing of Liver Biopsy Details(LIVER7)

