Urinalysis (clinical laboratory) / Urine culture / sensitivity ^f	X	X ^d	X	X	X	X	X	X	X	X	X ^d	X	X	X	X	X	X	
PVR	X		X	X	X	X	X	X	X	X		X	X	X	X	X	X	
Ultrasound (kidney/bladder)	X ^e											X	X	X	X	X	X	
Pregnancy test (Only females of reproductive potential) ^g	X	X ^d	X	X	X	X	X	X	X	X	X ^d	X	X	X	X	X	X	

CONFIDENTIAL

204947

Week	Treatment phase 1 If qualification for re-treatment criteria was met (Within 21days prior to re-treatment)	1st re-treatment	Treatment phase 2										With drawal			
			Re-treatment (1st)								If qualification for re-treatment criteria was met (Within 21days prior to re-treatment)	Re-treatment (2nd)				
			2	6	12	18 ^a	24 ^a	30 ^a	Study exit (48 weeks after 1st treatment)	2nd re-treatment		2	6	12 ^a	18 ^a	Study exit (48 weeks after 1st treatment)
Window	0	± 3 d	± 7 d	± 7 d	± 7 d	± 7 d	± 7 d	± 7 d	± 7 d	0	± 3 d	± 7 d	± 7 d	± 7 d	± 7 d	
Investigational product																
Treatment of antibiotic ^h		X									X					
Confirmation of day of re-treatment criteri ⁱ		X									X					
Treatment of investigational product		X ^j									X ^j					
Confirmation of qualification for re-treatment criteri ^{i,k}			X	X	X	X	X	X	X	X	X	X	X	X	X	
Concomitant meds / therapies	X	X	X	X	X	X	X	X	X	X	X	X	X	X	X	

d = day (s)

(a) Visit should not have occurred later than 48 weeks after 1st treatment. At 48 weeks after 1st treatment, study exit visit will be conducted.

(b) Bladder diary must have been completed for any 3 consecutive days in the week prior to the visit. The volume voided is recorded by subjects for one 24-hour period during the 3 day diary collection period.

(c) Measured only body weight

(d) Performed prior to treatment

(e) These examination can be completed at the Qualification for re-treatment visit or at any time prior to re-treatment

(f) Urine culture and sensitivity is performed by the central laboratory when urinalysis (dipstick) results were suggestive of a urinary tract infection

(g) If the result of urine pregnancy is suspicious, investigator (or sub-investigator) is able to conduct serum pregnancy test by central laboratory.

(h) First dose to be administered 1 (approximately 24 hours) to 3 days prior to study injection and continued for 1 to 3 days post injection (including the day of injection)

(i) Subjects who are not retreated will continue to visit at the scheduled study visit.

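### Urinalysis taken before the injection on a re-treatment day is assigned to the new GSK1358820 cycle, or to no cycle, and can become that cycle's worst-case result

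*SAP*

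**What the plan says.** Section numbers are those of the amended SAP.

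- **Timing of the sample.** The schedule reproduced in SAP 11.2.1 (Table 3; Protocol 7.1, Table 2) has a row "Urinalysis (clinical laboratory) / Urine culture / sensitivity". In both re-treatment columns this row carries the footnote "d) Performed prior to treatment". The row is the source of the protein and occult-blood results (Protocol Table 3).
- **Cycle boundaries for safety.** In SAP 11.4.1.2, TC1 ends strictly before the date of the second treatment when there is one; this bound uses the date only. For placebo-first subjects GTC1 then opens with the condition "2nd treatment Date /Time ≤ AE Start Date / Time", which includes the re-treatment day. GTC2 for GSK1358820-first subjects opens in the same way, and cycles that open at the third treatment follow the same pattern.
- **Rule for data other than adverse events.** The notes to 11.4.1.2 say that the AE start date "will be replaced with the date of measurement, unless otherwise specified". No measurement time is mentioned. A separate note asks for the time to be considered on the re-treatment date, but it names AE start time only.
- **Display.** SAP 8 presents urinalysis as the worst post-baseline result in each phase and not by visit, and measures change from study baseline. SAP 8.3 adds: "The determination of the worst case post-baseline takes into account both planned and unscheduled assessments". Table 3.114 gives this summary for the GSK1358820 cycles in population SP1, at the final analysis only.
- **Protection for a dosing-day sample.** SAP 5.2 treats Day 1 assessments without a recorded time as taken before the first dose and uses them as baseline. Nothing equivalent covers a re-treatment day.

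**The concern.** A worst-case summary for a GSK1358820 cycle should hold results obtained after that cycle's injection. Under the rule as written, a sample scheduled before the injection can supply the worst case. This is clearest for placebo-first subjects in GTC1: a protein or occult-blood result obtained before any exposure to GSK1358820 can be reported under the first GSK1358820 cycle. GSK1358820-first subjects have no such extra sample in GTC1, because their dosing-day sample is the baseline. The two columns of Table 3.114, and the total that pools them, therefore count samples by different rules. A subject with no later urine sample could also enter the denominator, which requires only some post-baseline result.

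At stake is the accuracy of a table that supports the repeated-dose safety objective.

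**Working it through.** The plan states no figure on this point, so there is none to reproduce. The check applies the printed inequalities to a test case and then illustrates the possible size.

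**Step 1. Classify one sample.** Take first treatment on Day 1, second treatment on Day 85 at 10:00, and a urine sample on Day 85 at 09:00 from a placebo-first subject.

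| Rule | Condition | Result |
|---|---|---|
| Safety TC1 (date only) | 85 < 85 | false: not in TC1 |
| Safety GTC1, by date | 85 ≤ 85 | true: in GTC1 |
| Safety GTC1, by date/time | 10:00 ≤ 09:00 | false: not in GTC1 |
| Efficacy TC1 (11.4.1.1) | 1 < 85 ≤ 85 | true: in TC1 |

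By date, the pre-injection sample moves into the GSK1358820 cycle. By date/time it leaves that cycle, but the date-only upper bound of TC1 still rejects it, so it has no cycle. Neither reading places it in the cycle in which it was taken. The efficacy phases put the same day in TC1.

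**Step 2. Follow it into the table.** The baseline is the study baseline, so the sample counts as post-baseline. Urinalysis is shown by phase and not by visit, so no Week 0 label sets it apart. SAP 8.3 takes planned and unscheduled samples and excludes neither pre-injection nor re-treatment-day results. The criteria for the day of re-treatment (Protocol 5.3) require a dipstick negative for nitrites and leukocyte esterase; they do not screen protein or occult blood.

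**Step 3. What the sample represents.**

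- Placebo-first, GTC1: before any GSK1358820.
- Placebo-first, GTC2: after one GSK1358820 dose, credited to the wrong cycle.
- GSK1358820-first, GTC2 and GTC3: after one or two doses, credited to the wrong cycle.

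**Step 4. Illustrative size.** Let p be the chance that one sample shows an increase over baseline, and k the number of samples after the injection. If samples are independent, the chance of Any Increase is 1 − (1 − p)^k without the extra sample and 1 − (1 − p)^(k+1) with it. The difference is p(1 − p)^k. The schedule gives k from 3 (re-treated at week 36: weeks 2, 6 and exit) to 7 (re-treated at week 12 and not again: weeks 2, 6, 12, 18, 24, 30 and exit). The values of p are assumptions.

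| p | k = 3 | k = 7 |
|---|---|---|
| 2% | 5.9% to 7.8% (+1.9) | 13.2% to 14.9% (+1.7) |
| 5% | 14.3% to 18.6% (+4.3) | 30.2% to 33.7% (+3.5) |
| 10% | 27.1% to 34.4% (+7.3) | 52.2% to 57.0% (+4.8) |
| 20% | 48.8% to 59.0% (+10.2) | 79.0% to 83.2% (+4.2) |

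The range is 1.7 to 10.2 percentage points. It applies to a column in which every subject has the extra sample, such as placebo-first GTC1. In the GTC1 total it is diluted by GSK1358820-first subjects, who have none.

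**The case against.** The strongest reply is that the re-treatment lower bounds are printed as date/time. If the time element is kept for laboratory data, a pre-injection sample never reaches the new cycle and nothing on drug is inflated. This is a fair reading and it limits the claim: entry into the GSK1358820 cycle is not the only possible outcome. It does not rescue the rule, because the sample is then lost from every cycle, and the substitution note speaks only of the date of measurement.

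Four stronger inferences are tempting, and the documents do not support them.

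- **That re-treatment-day safety data in general are affected.** Vital signs have a labelled Week 0 row in the cycle tables. Chemistry, hematology, ECG and PVR are displayed by visit, with no Week 0 row. The exposure is mainly Table 3.114.
- **That an adverse event starting before the injection falls in no cycle.** The inequalities taken alone give that result. The note on AE start time largely answers it, since it shows the intention to split the day at the injection. What remains is that the TC1 upper bound, and the lower bound of the Overall period for placebo-first subjects, are still written by date only.
- **That the rule makes the two columns non-comparable.** They already differ: one is the randomised blinded cycle, the other an open-label cycle entered by qualification.
- **That the efficacy note settles the same-day question for all data.** The remark in 11.4.1.1 that "this can be regarded as prior to treatment according to study protocol" concerns the first treatment date. The relevant contrast is the efficacy inequality itself.

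The size is also open to challenge. Repeated protein and occult-blood results in one person are likely to be correlated, which shrinks the increment. The pre-injection sample may also have a lower rate than later ones, because re-treatment requires a negative infection dipstick and no UTI symptoms. The sample matters to Any Increase only if no later sample in the cycle shows an increase.

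**Conclusion.** The point stands in a limited form. SAP 11.4.1.2 misplaces the scheduled pre-injection urinalysis on re-treatment days under either reading of its bounds. On the date-only reading, which is the literal one for laboratory data, the sample can become the worst case of the new cycle in Table 3.114. It precedes all GSK1358820 only for placebo-first subjects in GTC1; otherwise the error is one of cycle.

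The size cannot be established, because the documents give no per-sample rate. The 2 to 10 points on Any Increase rest on assumed rates of 2% to 20%, 3 to 7 later samples, independence, and equal rates before and after injection. A smaller effect is likely.

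The table is descriptive and no test is planned on it. The primary efficacy analysis is untouched. The double-blind TC1 urinalysis table gains no misplaced sample; it only loses the re-treatment-day one. The point is worth correcting before the final analysis, and it does not threaten the trial's main conclusions.

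**What to change.** In SAP 11.4.1.2:

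1. State that safety measurements other than adverse events that are scheduled before the injection on a re-treatment date, or timed before it where a time is recorded, belong to the preceding cycle and are excluded from the new cycle's worst case.
2. State that measurements after the injection on that date belong to the new cycle. Sending the whole day to the preceding cycle would be wrong: subjects stay for observation after the injection, PVR may be measured whenever clinically needed, and unscheduled urine results count in the worst case. A result obtained after GSK1358820 could then be reported under placebo.
3. Keep the labelled Week 0 rows for vital signs.
4. For adverse events, write the TC1 upper bound and the Overall lower bound by date and time, as the existing note intends. Give the upper bounds of GTC1 and GTC2 the same form, so that each event falls in exactly one cycle.

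The cost is a few lines of text and a change to the phase derivation that uses the scheduled pre-dose status or the time. No new data or visits are needed. The TC1 urinalysis summary (Table 3.113) will gain the re-treatment-day sample for re-treated subjects. That table is produced at both the interim and the final analysis, so the report should say which rule each used.
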